**Table 5.4-2 Criteria for Assessing Maximum Tolerated Doses (MTDs) at Level 2**

Incidence of DLTs in the first 3 patients at Level 2, and the decision	Incidence of DLTs when 3 patients are additionally enrolled at Level 2 (a total of 6 patients), and the decision
0 of 3 patients: Terminate the study (MTD: 40 mg).	—
1 of 3 patients: Additionally enroll 3 patients at Level 2.	1 of 6 patients or 2 of 6 patients: Terminate the study (MTD: 40 mg). 3 of 6 patients or 4 of 6 patients: Terminate the study (MTD: 20 mg).
2 of 3 patients or 3 of 3 patients: Terminate the study (MTD: 20 mg).	—

If any of the criteria provided in “5.4.4 Enrollment of Additional Patients” is met at Level 1 and any patient is excluded from DLT assessment, information on AEs occurring in the concerned patient, etc. should be taken into consideration to assess whether to proceed to Level 2 or not.

Whether it is necessary or not to establish a new level, in addition to Level 1 and Level 2, will be determined through discussion between the investigator and the sponsor. The medical expert will be consulted as needed.

#### **5.4.3 Determination of Maximum Tolerated Doses**

The MTD will be determined in accordance with the assessment criteria given in Table 5.4-2.

#### **5.4.4 Enrollment of Additional Patients**

If any of the following apply, the need to enroll additional patients at the level or not will be determined through discussion between the investigator and the sponsor. The medical expert will be consulted as needed. If enrollment of additional patients is determined, the patients meeting any of the following will be excluded from DLT assessment.

- A patient is found to be ineligible after registration.
- A patient has taken quizartinib for the following number of days during the DLT assessment period.
  - The number of days of quizartinib administration is  $\leq 9$  for patients who have completed remission induction therapy in Cycle 1
  - The number of days of quizartinib administration is  $\leq 9$  both in Cycle 1 and Cycle 2 for patients who have proceeded to remission induction therapy in Cycle 2.
- A patient takes quizartinib at a higher dose at once than the dose given at the participating level during the DLT assessment period.

- The investigator or the sponsor considers it difficult to assess DLTs in a patient because some procedures during the DLT assessment period have not been performed appropriately.
- A patient is withdrawn from the study because the patient meets the criteria specified in “5.6 Withdrawal Criteria” during the DLT assessment period (except in case the study is terminated due to DLTs).
- Enrollment of additional patients is otherwise considered necessary for safety evaluation.

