**5.3.2 Emergency Procedures and Management in the Event of Quizartinib Overdose**

In the event of overdose of quizartinib, the investigator or subinvestigator should immediately assess the patient's condition, and if any symptoms are found, immediately provide appropriate intervention and supportive therapy. The investigator and sponsor will discuss and decide whether the patient may continue study participation or not, taking the status of overdose and the subsequent course of the patient into consideration. For overdose occurring during the DLT assessment period, the patient will be excluded from the DLT assessment (refer to “5.4.4 Enrollment of Additional Patients”).

In an overseas Phase 1 study (Study CP0001), quizartinib was tested with treatment cycles of intermittent dosing (14 days on the drug followed by 14 days of rest) at 450 mg/day, and 28-day continuous dosing at 200 and 300 mg/day. No DLTs occurred in 6 patients receiving intermittent dosing at 450 mg/day, whereas Grade 3 QTc

prolongation was seen in 1 of 17 patients on continuous dosing at 200 mg/day and in 3 of 8 patients on continuous dosing at 300 mg/day.

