#### **11.1.3 MTD Analysis Set**

The MTD Analysis Set is defined as patients who received at least 1 dose of any of the study drug, cytarabine, and the anthracycline drug, but excludes the patients listed below.

- Patients whose DLT assessment has not been performed appropriately because some of the procedures during the DLT assessment period are missing for other reasons than adverse drug reactions (eg, worsening of the clinical condition due to progression of the primary disease, AEs that are assessed as not related to the study drug)
- Patients who have taken quizartinib for the following number of days during the DLT assessment period
  - The number of days of quizartinib administration is  $\leq 9$  for patients who have

completed remission induction therapy in Cycle 1

- The number of days of quizartinib administration is  $\leq 9$  both in Cycle 1 and Cycle 2 for patients who have proceeded to remission induction therapy in Cycle 2.

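### Sections 5.3.2, 5.4.4 and 11.1.3 disagree on who counts for DLT, and a patient whose DLT cut dosing short can drop out of the DLT analysis

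*Combined protocol and SAP*

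**What the plan says.** **Section 5.4.4** gives six triggers. When one applies, "the need to enroll additional patients at the level or not will be determined through discussion between the investigator and the sponsor". Exclusion then hangs on that decision: "If enrollment of additional patients is determined, the patients meeting any of the following will be excluded from DLT assessment". The triggers are:

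- ineligibility ("A patient is found to be ineligible after registration");
- 9 or fewer days of quizartinib;
- overdose ("A patient takes quizartinib at a higher dose at once than the dose given at the participating level during the DLT assessment period");
- procedures not properly performed;
- withdrawal ("A patient is withdrawn from the study because the patient meets the criteria specified in" Section 5.6, with an exception for termination due to DLTs);
- a general clause: "Enrollment of additional patients is otherwise considered necessary for safety evaluation".

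**Section 5.3.2** says of overdose: "For overdose occurring during the DLT assessment period, the patient will be excluded from the DLT assessment". It attaches no condition, but it does point to 5.4.4.

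**Section 11.1.3** defines the MTD Analysis Set as "patients who received at least 1 dose of any of the study drug, cytarabine, and the anthracycline drug, but excludes the patients listed below". Two groups are listed: patients whose DLT assessment was inadequate because procedures were missing for reasons other than adverse drug reactions, and patients with 9 or fewer quizartinib days. It cites neither 5.3.2 nor 5.4.4.

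**How these are used.** Section 11.3.2 runs the DLT analyses on the MTD Analysis Set. Section 5.4.3 takes the MTD from Table 5.4-2. The text below that table asks that AEs of a patient excluded at Level 1 be weighed before proceeding to Level 2. No matching sentence covers exclusions at Level 2.

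**The concern.** Two counts of DLTs come out of this plan: the one that drives Tables 5.4-1 and 5.4-2, and the one in the report. They are governed by different lists, and one list operates only after a discretionary decision. With three to six patients per level, a single patient handled differently is visible in the result. Determining the dose for later development is part of the primary objective, so the reported DLT table should support the dose decision.

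The short-exposure rule raises a further problem. Section 5.5 interrupts quizartinib for related Grade 3 non-hematological toxicity in induction, and at Level 2 for QTcF prolongation of Grade 3 or higher. Such events are ordinarily DLTs under 5.4.1. The interruption caused by the DLT can then be what makes the patient non-evaluable.

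**Working it through.** **1. The rules side by side**

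| Criterion | 5.3.2 | 5.4.4 | 11.1.3 |
|---|---|---|---|
| Overdose | Excluded, no condition | Excluded if additional enrolment is decided | Not listed |
| Ineligible | Not addressed | Same condition | Not listed |
| 9 or fewer days | Not addressed | Same condition; no DLT exception | Excluded, no condition; no DLT exception |
| Procedures missing or poorly done | Not addressed | Same condition; no DLT exception | Excluded unless due to adverse drug reactions |
| Withdrawal under 5.6 | Not addressed | Same condition; DLT terminations exempt | Not listed as such |
| General clause | Not addressed | Reason to enrol; effect on exclusion unclear | Not listed |

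An overdosed patient who is not replaced is therefore out under 5.3.2, not excluded under 5.4.4, and not excluded for the overdose under 11.1.3.

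**2. The plan's own figures.** Two levels × 3 = 6 and two levels × 6 = 12, which reproduces the planned 6 to 12 patients if both levels open and nobody is replaced. Replacements could take the total above 12. The decision tables have rows for denominators of 3 and 6 only.

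**3. Short exposure.** Cycle 1 dosing runs from Day 8 to Day 21: 21 − 8 + 1 = 14 doses. Missing 5 leaves 14 − 5 = 9, which meets the threshold. Section 5.5 allows up to 28 days for a Grade 3 event to resolve, so losing 5 doses is easily possible. A patient who goes on to Cycle 2 is caught only if exposure is 9 days or fewer in both cycles.

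**4. What the two counts can look like**

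- Three counted patients without a DLT, plus one overdosed patient with a DLT who is replaced: 0/3 for escalation, 1/4 (25%) in the MTD Analysis Set.
- Level 2, two DLTs in six counted patients, plus one replaced overdosed or ineligible patient with a DLT: 2/6 for the decision (MTD 40 mg), 3/7 (43%) in the set.
- One DLT in the first three, in a patient with 9 or fewer days who is not replaced: 1/3 for the decision (enrol three more), 0/2 in the set for the same three.

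The discrepancy can thus run in either direction.

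**5. How much one patient matters.** Let p be the true DLT probability, q = 1 − p, and A = q³ + 3pq² (at most one DLT in three). A level passes the tables with probability q³ + 3pq²·A. If the first DLT patient at a level is excluded and replaced once, this becomes q³ + 3pq³ + 6p²q²·A. At p = 0.3, A = 0.343 + 0.441 = 0.784, giving 0.343 + 0.441 × 0.784 = 0.689 and 0.343 + 0.309 + 0.265 × 0.784 = 0.859.

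| Assumed p | All DLTs counted | One DLT patient replaced |
|---|---|---|
| 0.1 | 0.965 | 0.995 |
| 0.2 | 0.856 | 0.957 |
| 0.3 | 0.689 | 0.859 |
| 0.4 | 0.496 | 0.699 |
| 0.5 | 0.312 | 0.500 |

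The second column of results shows what such a replacement would do if it happened. It does not forecast that it will.

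**6. How often a mismatch could arise.** If each patient independently meets a criterion found only in 5.4.4 with probability e, the chance of at least one is 1 − (1 − e)ⁿ. For e = 5%, 10% and 20% this is 27%, 47% and 74% with 6 patients, and 46%, 72% and 93% with 12. The documents give no value for e or p; all are assumptions.

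**The case against.** Several points on the other side are sound.

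- A reader might see three independent rules. Section 5.3.2 cross-refers to 5.4.4, which has a matching overdose trigger, so those two may be one rule loosely worded. The conditional and unconditional wording still conflict, but the gap that matters for reporting is 5.4.4 against 11.1.3.
- A reader might infer that the mismatch changes the MTD. It does not automatically do so: the MTD comes from Table 5.4-2, and 11.1.3 feeds the DLT and baseline tables.
- A reader might infer that an excluded DLT vanishes from the escalation decision. At Level 1, AEs of excluded patients must be considered. That safeguard carries no decision rule and does not reach Level 2, where the MTD is set.
- It would be too broad to say that all withdrawn patients stay in the MTD Analysis Set. The missing-procedures exclusion removes some, and Section 11.1 removes major GCP violators from every set. In 5.4.4 itself, termination due to a DLT is not a ground for exclusion.
- The general clause describes no patient attribute, so it is arguable whether anyone can meet it and be excluded. It needs clarifying; it is not proof of an open licence to drop patients.
- The study is open-label, but 5.4.4 does not say when the replacement decision is taken. Deliberate outcome-driven replacement cannot be read from the text.

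Section 11 is an outline that defers detail to the Statistical Analysis Plan, and no fuller text on this point is available for this check. Sponsor eligibility review before registration and hospitalization in the DLT period should make ineligibility and overdose less likely. Neither removes the inconsistency or the missing DLT exception.

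**Conclusion.** The concern holds as an inconsistency in the DLT-evaluability rules. Overdose and ineligibility are handled in 5.4.4 but absent from 11.1.3. Overdose is unconditional in 5.3.2 and conditional in 5.4.4. Short exposure is conditional in 5.4.4 and unconditional in 11.1.3. Following the plan exactly can give a reported DLT count that differs by one patient, or more, from the count used for the dose decision.

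The more serious consequence is that a patient with a DLT who misses 5 or more of 14 Cycle 1 doses can leave the DLT analysis, unless a second induction cycle brings at least 10 days of dosing. Under 5.4.4 the same patient can also leave the decision count if additional enrolment is decided.

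The documents do not support the stronger conclusion that the MTD rule itself is wrong or that replacement will be used to remove DLTs. The counting examples follow from the wording; the probabilities rest on assumed rates.

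**What to change.** - Write one list of DLT-evaluability criteria, use it identically in 5.4.4 and 11.1.3, and have 5.3.2 refer to it.
- Apply the list whether or not a replacement is enrolled, so that evaluability and replacement are separate decisions.
- State that a patient with a DLT is not excluded for short exposure or missing procedures.
- Clarify that the last trigger in 5.4.4 is a reason to add patients only.
- Extend the sentence below Table 5.4-2 on AEs of excluded patients to Level 2.
- Reconcile 5.3.2, 5.4.4 and 11.1.3 on how an overdosed patient with a DLT is handled, and state which rule takes precedence. A blanket statement that DLT patients always count would collide with the overdose exclusion.

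This is a change of wording only, with no extra procedures and no change to the planned 6 to 12 patients. The downside is slightly less flexibility in replacing patients.

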## **5.4 Assessment of Dose-limiting Toxicity**

### **5.4.1 Definition of Dose-limiting Toxicities**

The DLT assessment period is from the start day of quizartinib administration in Cycle 1 of remission induction therapy to the preceding day of Day 1 of Cycle 1 of consolidation therapy (induction phase), and a DLT is defined as any toxicity among AEs that occur during the above period that are assessed to be “related” to quizartinib, as listed below. The severity grade will be assessed according to the Common Terminology Criteria for Adverse Events (CTCAE) v4.0 Japanese version.

- $\geq$  Grade 3 non-hematological toxicities (except for the following)
  - Alopecia, anorexia, and fatigue
  - Grade 3 queasy, vomiting, or diarrhea that has improved to  $\leq$  Grade 2 within 7 days after the onset after treatment with antiemetic or antidiarrheal drugs
  - Grade 3 mucositis that has improved to  $\leq$  Grade 2 within 7 days after the onset
  - Grade 3 infections
  - Febrile neutropenia
- Hematological toxicities that have not resolved before Day 1 of Cycle 1 of consolidation therapy, as listed below
  - Peripheral neutropenia ( $< 500/\text{mm}^3$ )
  - Thrombocytopenia resulting from bone marrow aplasia or hypoplasia ( $< 20\,000/\text{mm}^3$ )

- $\geq$  Grade 3 thrombocytopenia associated with bleeding ( $< 50\ 000/\text{mm}^3$ )
- Grade 4 thrombocytopenia requiring blood transfusion ( $< 25\ 000/\text{mm}^3$ )

If there is a day when quizartinib cannot be taken due to any toxicity during the DLT assessment period, the investigator and the sponsor will discuss and decide whether to handle the toxicity as a DLT or not.

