## **5.5 Criteria for Temporary Discontinuation, Dose Reduction, and Resumption of Quizartinib**

- When the need arises to use drugs that may potentially prolong the QT/QTc interval or strong CYP3A4 inhibitors by necessity during the quizartinib treatment period: Quizartinib administration should be temporarily discontinued from the start to the end of use of the above-mentioned drugs. On the day when the quizartinib is resumed after interruption, vital sign measurement, 12-lead ECG, and laboratory tests will be performed before the start of quizartinib administration (refer to “6.2 Remission Induction Therapy” and “6.3 Consolidation Therapy”).
- When  $\geq$  Grade 3 QTcF prolongation occurs in a patient at Level 2: Quizartinib administration should be temporarily discontinued from the onset time of the above event.  
If the increase in QTcF recovers to  $\leq$  30 ms, compared with the value at registration, within 14 days after the onset, quizartinib administration will be resumed at a dose reduced to 20 mg/day.  
If the increase in QTcF does not recover to  $\leq$  30 ms, compared with the value at registration, within 14 days after the onset, the study for the relevant patient will be discontinued.  
\* If  $\geq$  Grade 3 QTcF prolongation occurs in a patient at Level 1, the study for the patient should be discontinued (refer to “5.6 Withdrawal Criteria”).
- When a DLT occurs (including cases in which it takes time to assess the causality with quizartinib, cytarabine, or the anthracycline drug but the toxicity can potentially be associated with quizartinib):  
If Grade 3 non-hematological toxicity (except QTcF prolongation) occurs during the induction phase and it is assessed to be “related” to quizartinib, quizartinib administration will be temporarily discontinued from the onset time of the event. If

the event resolves to Grade 1 within 28 days after the onset of the event and the investigator or subinvestigator decides it possible to resume quizartinib administration, quizartinib administration will be resumed.

If a Grade 4 non-hematological toxicity (except QTcF prolongation) occurs during the induction phase, the study for the relevant patient will be discontinued.

Once the dose of quizartinib is reduced, the dose should not be increased again to the original dose.

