## **5.6 Withdrawal Criteria**

The study treatment must be withdrawn for any of the following reasons:

- 1) Overt disease progression
- 2) Intolerable AEs including the following:
  - Grade 4 non-hematological toxicity for which the relationship to the study drug is assessed as “related”
  - (For patients at Level 1) Grade 3 or higher QTcF prolongation or DLT
  - (For patients at Level 2) Any AE that does not lead to a situation allowing the resumption of study treatment, as specified in “5.5 Criteria for Temporary Discontinuation, Dose Reduction, and Resumption of Quizartinib.”
- 3) The need of the second dose reduction in patients with a dose reduction of the study drug
- 4) Achievement of CR, CRp, or CRi in Cycle 2 or later of consolidation therapy, leading to the decision of the investigator or subinvestigator to introduce HSCT
- 5) Patient’s withdrawal of consent for study participation
- 6) Ineligibility found after registration in the study
- 7) Patient found to be pregnant after registration in this study
- 8) Poor patient compliance with study procedures, including failure to visit the study center as scheduled in the protocol
- 9) Other circumstances why the study cannot be continued in the investigator’s or subinvestigator’s opinion

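### Section 5.4.4 allows a Level 2 patient with a recorded DLT to be replaced and left out of the MTD count if later withdrawn for another reason

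*Combined protocol and SAP*

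**What the plan says.** Section 5.4.4 lists situations in which the investigator and the sponsor discuss whether to enroll more patients at a level. If they decide to do so, the consequence is firm: "If enrollment of additional patients is determined, the patients meeting any of the following will be excluded from DLT assessment". The fifth item on the list is withdrawal under 5.6 "during the DLT assessment period (except in case the study is terminated due to DLTs". The second item is nine or fewer days of quizartinib, and it has no exception for DLTs.

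Other sections determine how far the fifth item reaches:

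- Section 5.4.1 runs the period from the first quizartinib dose "to the preceding day of Day 1 of Cycle 1 of consolidation therapy (induction phase". It gives no end for a patient who never starts consolidation.
- Section 5.6 includes "Overt disease progression", withdrawal of consent and "Other circumstances why the study cannot be continued in the investigator’s or subinvestigator’s opinion". It also has the line "For patients at Level 1) Grade 3 or higher QTcF prolongation or DLT", so a DLT at Level 1 is itself a reason for withdrawal.
- Section 5.5 lets dosing resume after a related Grade 3 non-hematological toxicity if "the event resolves to Grade 1 within 28 days after the onset of the event" and the investigator agrees. At Level 2 it also allows a restart at a reduced dose once QTcF prolongation of Grade 3 or higher has recovered. Section 15.3 plans for re-consent before dosing resumes after a DLT.
- Section 5.4.2 asks that adverse events in patients excluded at Level 1 be weighed before moving to Level 2. It says nothing comparable for Level 2.
- Section 11.1.3 defines the MTD Analysis Set, which 11.3.2 uses for DLT analyses. It excludes "Patients whose DLT assessment has not been performed appropriately because some of the procedures during the DLT assessment period are missing", provided the cause is not an adverse drug reaction, and names disease progression as an example cause. It repeats the nine-day rule. Withdrawal as such is not on its list.

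**The concern.** The exception protects a DLT only when the DLT is what ended the patient's participation. Sections 5.5 and 15.3 expect some patients to carry on after a DLT. If such a patient later leaves for an unrelated reason, the event is on record, was judged related to quizartinib and met the definition, yet the wording lets the patient and the DLT leave the count together.

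In Tables 5.4-1 and 5.4-2 a denominator of three or six decides the outcome, so one DLT more or less can change the MTD. The decision to replace is made by discussion in an open-label study, when DLT status can already be known, and 5.4.4 does not say how a recorded DLT should weigh in it.

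The nine-day rule raises the same problem by another route. A cycle has 14 quizartinib days, so a DLT that costs five or more of them leaves nine or fewer (14 − 5 = 9). On the literal wording, the toxicity that stopped dosing can then make the patient non-evaluable. In 11.1.3 that exclusion is not even discretionary.

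**Working it through.** **Plan's own figure.** The sample size of 6 to 12 reproduces: two levels of three give 6, and two levels of six give 12. The documents give no DLT rate and no withdrawal rate, so every rate below is an assumption.

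**Route by which a DLT is lost.** All four steps are needed:

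1. A Level 2 patient has a DLT that resolves as 5.5 requires.
2. Quizartinib is resumed.
3. The patient is withdrawn for a non-DLT reason before Day 1 of consolidation.
4. The investigator and sponsor decide to enroll a replacement, and exclusion follows.

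There is time for step 3. After the last Cycle 1 dose on Day 21, an on-schedule patient has Days 22 to 28, or 7 days, still inside the period. The whole period is 28 − 8 + 1 = 21 days with one induction cycle and 56 − 8 + 1 = 49 days with an undelayed second cycle. If Cycle 2 starts 56 days after Day 1 of Cycle 1 it ends on Day 84, and the period is 84 − 8 + 1 = 77 days.

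**Decision rule in Table 5.4-2.** Let p be the true DLT rate and q = 1 − p. The chance of at most one DLT in three patients is a = q³ + 3pq². The chance that Level 2 gives an MTD of 40 mg is q³ + 3pq²·a. At p = 0.40, a = 0.216 + 0.432 = 0.648, and the chance is 0.216 + 0.432 × 0.648 = 0.496.

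**Effect of removing one patient with a DLT** from the first three at Level 2:

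- Case A, one DLT in three. If the patient is kept, P(MTD 40 mg) = a. If replaced, it is q + p·a. At p = 0.40 that is 0.648 against 0.6 + 0.4 × 0.648 = 0.859.
- Case B, two DLTs in three. If both are kept, the MTD is 20 mg, so P(MTD 40 mg) = 0. If one is replaced, it is q·a. At p = 0.40 that is 0.6 × 0.648 = 0.389.

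| Assumed p | Case A kept | Case A replaced | Case B kept | Case B replaced |
|---|---|---|---|---|
| 0.20 | 0.896 | 0.979 | 0 | 0.717 |
| 0.33 | 0.745 | 0.916 | 0 | 0.499 |
| 0.40 | 0.648 | 0.859 | 0 | 0.389 |
| 0.50 | 0.500 | 0.750 | 0 | 0.250 |

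These figures are conditional on the event having happened. They do not say how often it would.

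**Average effect.** Let w1 and w0 be the assumed shares of patients dropped among those with and without a DLT. The counted rate is p(1 − w1) / [p(1 − w1) + (1 − p)(1 − w0)]. At p = 0.40:

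| w1 | w0 | Counted rate | P(MTD 40 mg) |
|---|---|---|---|
| 20% | 20% | 40.0% | 0.496 |
| 20% | 0 | 34.8% | 0.597 |
| 40% | 0 | 28.6% | 0.715 |
| 0 | 20% | 45.5% | 0.393 |

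The shift is zero when dropping is unrelated to DLT status, and otherwise can go either way.

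**The case against.** The strongest reply is that section 3 introduces 5.4.4 as the route for patients in whom DLT cannot be assessed properly. Read that way, a patient with a recorded DLT would not be replaced at all, and because replacement needs a joint decision, sensible people would not use it so. That is a fair account of the intent. But the fifth item does not repeat the condition, and once a replacement is agreed the exclusion is mandatory.

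The reply also rightly limits the scope:

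- A reader might infer that any withdrawn patient is dropped, or that the DLT count is bound to follow leukemia outcome. The text supports neither. Terminations due to DLTs are exempt, which covers DLT withdrawals at Level 1 and unresolved DLTs at Level 2. Lack of remission is not a listed criterion in 5.6 and would have to enter through investigator judgement.
- A reader might infer that 11.1.3 keeps every patient whom 5.4.4 drops. It does not. Its missing-procedures item reaches patients whose assessments stopped because of progression. The lists differ mainly for withdrawn patients with nothing missing.
- A reader might infer that DLT-free patients with ten or more dosing days must be counted. The nine-day item sets a floor for too little exposure and does not declare more to be enough. Hematological DLTs are read against Day 1 of consolidation, and sections 1.3.2 and 1.4 describe delayed neutrophil and platelet recovery. Counting such patients as non-events could lower the DLT rate, so treating them as non-evaluable is defensible.

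The one-sided rows of the average-effect table assume that only one kind of patient is dropped. Since many DLT patients would fall under the exception, the larger values of w1 are extreme.

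**Conclusion.** The gap is real but narrow. No sentence in the plan says that a recorded DLT always counts. At Level 2, where Table 5.4-2 fixes the MTD, a patient with a resolved DLT who later leaves for another reason may be removed from the count, and no review of excluded patients' adverse events applies there. The nine-day items in 5.4.4 and 11.1.3 have the same omission.

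The size depends on assumed rates. In the sharpest case, two DLTs in three with one patient replaced, the chance of an MTD of 40 mg moves from 0 to between 0.25 and 0.72 over assumed DLT rates of 50% down to 20% (0.39 at 40%). This takes the replacement and any further patients to have the same independent DLT risk. How often the case would arise cannot be worked out from the documents, and the text does not show that the count would in fact be biased.

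**What to change.** State in both 5.4.4 and 11.1.3 that a patient with a recorded DLT is always counted, whatever the later reason for withdrawal and however many days quizartinib was taken. Then reconcile the two exclusion lists, so that the count used for the dose decision and the MTD Analysis Set contain the same patients. The separate exclusion for overdose in 5.3.2 is not at issue here.

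Leave to the sponsor whether DLT-free, sufficiently exposed patients who never reach consolidation are counted. Report them in a sensitivity count beside the main one, so that a reader can see whether the decision depends on that choice.

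The cost is a sentence in each section plus the alignment of the lists. No dose or treatment rule changes. The small downside is that a DLT in a patient who would otherwise have been replaced still counts, which makes the decision slightly more conservative.
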